9.6. Safety Variables and Analysis

9.6.1. Safety Variables

Safety variables are as follows:

- Ocular and non-ocular AE monitoring
- BCVA

- Biomicroscopy
- Intraocular pressure
- Dilated fundus exam
- IP comfort assessment

9.6.2. Safety Analysis

Safety and IP comfort data will be presented in tables of descriptive statistics and frequency distribution. All summary tables will be supported with individual subject data listings.

AEs that occur during the screening/run-in period (Visit 1/Day-14 ± 2 to Visit 2/Day 1) will be summarized separately from AEs that occur from the first dose of double-masked treatment on Day 1 to the Day 84 Visit or Early Discontinuation.

The primary safety analysis will summarize ocular and non-ocular treatment-emergent adverse events (TEAEs) using discrete summaries at the subject level by system organ class and preferred term for each treatment group. A TEAE will be defined as occurring after the first dose of IP. Serious adverse events (SAEs) and treatment-related ocular and non-ocular TEAEs will be summarized similarly. Ocular and non-ocular TEAEs will also be summarized by severity.

Biomicroscopy and dilated indirect ophthalmoscopy measures will be summarized by tabulating the distribution of score shifts between baseline and post-baseline assessments

Best-corrected visual acuity (BCVA; logMAR) and IOP (mm Hg) will be summarized at each visit, using continuous and discrete summary statistics, including change from baseline and the proportion of study eyes with pre-defined increases from baseline, specifically, eyes with a 3-line decrease in BCVA or eyes with ≥ 10 mm Hg increase in IOP.

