5.2. Selection, Timing and Administration of Dose for Each Patient

Subjects will be randomized to treatment with 1 of 3 concentrations (0.1%, 1.0% and 3.0%) of SDP-4 Ophthalmic Solution or vehicle which will be administered to each eye BID, approximately 12 hours apart, for 84 days.

Subjects (or their caregiver, if the subject is not able to self-administer the IP) will administer IP topically OU BID for 84 days. At the Screening and Baseline visits, site personnel will instruct the subject (or caregiver) in topical ocular drop administration procedures. After instilling a drop in each eye, the used single-use dose (SUD) should be stored in the storage container provided by site personnel and placed back in the box.

Twice each day, approximately 12 hours apart, the subject (or caregiver) will open a new SUD and administer 1 drop to each eye, store the used SUD in the foil pouch, and place it in the box (or storage container) for return to the clinical site so accountability can be documented in the source document and electronic case report form (eCRF). All IP, including the box, used SUDs/foil pouches and any unopened SUDs will be returned to the clinical site where the used and unopened IP will be documented at Visits 2 through 7.

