5.7. Packaging and Labeling

The IP will be filled into blow-fill-seal (BFS) containers composed of low density polyethylene (LDPE). The individual cartridges of 5 SUDs will be seal packed into a foil pouch. The foil-wrapped cartridges will be packaged 7 at a time into a cardstock storage box that will contain a total of 35 SUDs for the 2-week run-in period. The foil-wrapped cartridges will be packaged 16 at a time into a cardstock storage box that will contain a total of 80 SUDs dispensed monthly at Visits 2, 5 and 6 during the randomized treatment period. A label bearing the required IP labeling information per Code of Federal Regulations (CFR) Part 312, Section 312.6 will be added on the outside of the foil wrapping and the outside of the IP storage box.

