5.9. Investigational Product Dispensing and Retention at Study Site

At Visit 1/Screening, if the eligibility criteria are met, vehicle solution for the screening/run-in period will be dispensed to the subject with instructions to return the used and unused IP at Visit 2/Day 1. When the run-in study materials are returned by the subject, accountability will be performed and the box will be retained at the site in a secured location.

At Visit 2/Day 1, Kit 1 will be dispensed after the subject is randomized. Kits 2 through 3 will remain in a secured location at the site. The subject will be instructed to return the box along with all used and unused IP study materials at Visit 5/Day 28.

At Visit 5/Day 28, when Kit 1 is returned by the subject, accountability will be performed and the kit will be retained at the site in a secured location. The site will dispense Kit 2 to the subject according to randomization number with instructions to return the box along with used and unused IP study materials at Visit 6/Day 56.

At Visit 6/Day 56, when Kit 2 is returned by the subject, accountability will be performed and the kit will be retained at the site in a secured location. The site will dispense Kit 3 to the subject with instructions to return the box along with used and unused IP study materials at Visit 7/Day 84.

At Visit 7/Day 84, when Kit 3 is returned by the subject, accountability will be performed and the kit will be retained at the site in a secured location for the clinical research associate (CRA) to perform IP accountability and reconciliation. At the end of the study, the site or CRA will ship the IP study materials back to the packager for destruction.

Note: If at any visit, the subject complains of persistent dry eye symptoms and a supply of artificial tears is provided, the subject must return all used and unused artificial tears at *each* subsequent visit so the site can perform accountability to assess the use of artificial tears/resupply artificial tears as needed.

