6.4. Adverse and Serious Adverse Events

6.4.1. Definition of Adverse Events

6.4.1.1. Adverse Event (AE)

An AE is any untoward medical occurrence in a clinical study subject administered an IP that does not necessarily have a causal relationship with this treatment. An AE can therefore be any unfavorable and unintended sign (for example, an abnormal laboratory finding), symptom, or disease temporally associated with the use of an IP, whether or not considered related to this IP.

Note: IP in this study refers to all concentrations of SDP-4 and to the vehicle (control).

Medical conditions/diseases present before starting the investigational treatment are only considered AEs if they worsen after starting the investigational treatment. Abnormal test results constitute AEs only if they induce clinical signs or symptoms, are considered clinically significant, or require therapy.

The occurrence of AEs should be sought by open-ended questioning of the subject at each visit during the study. At each clinic visit, study personnel should ask the following question: "Have you had any problems since your last visit?" Adverse events also may be detected when they are volunteered by the subject during or between visits or through study assessments.

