6.6. Recording Adverse Events

Adverse events (AEs) spontaneously reported by the subject and/or in response to an open question from the study personnel or revealed by observation, regardless of severity or potential association with the IP or study procedures, will be recorded in the eCRF. Changes from baseline assessments that are part of the disease being studied will not necessarily be recorded as AEs unless the Investigator deems them as such. Investigators are advised to consider reporting an increase in IOP of 10 mmHg or greater, or a visual acuity decrease of 3 lines EDTRS (15 letters) or greater as an AE. If ongoing at the time of the subject's last study visit, Investigators should follow the event until the subject has returned to baseline or the event has resolved.

All AEs that occur following consent and until the final study visit (Visit 7/Day 84) should be collected and recorded on the AE eCRF page. AEs that occur during the screening/run-in period (Visit 1/Day-14 ± 2 to Visit 2/Day 1) will be summarized separately from AEs that occur from the first dose of double-masked treatment on Day 1 to the Day 84 Visit or Early Discontinuation. Serious adverse events (SAEs) will be followed until the event is resolved or stabilized.

The AE term should be reported in standard medical terminology when possible. For each AE, the Investigator will evaluate and report the following:

- Onset (date)
- Resolution (date)
- Severity grade (mild, moderate, severe)
- Relationship to IP (not suspected, suspected)
- Action taken (none, IP temporarily interrupted, IP permanently discontinued; concomitant medication taken; hospitalization/prolonged hospitalization; other)
- Serious outcome (yes/no)

The severity grade should be determined by the Investigator using the definitions below:

- **Mild:** Discomfort noticed but no disruption of normal daily activity
- **Moderate:** Discomfort sufficient to cause interference with normal daily activity
- **Severe:** Incapacitating, with inability to perform normal activities

It is important to distinguish between serious and severe AEs. Severity is a measure of intensity (as defined directly above) whereas seriousness is defined by the criteria under Section 6.4.1.2. An AE of severe intensity may not be considered serious.

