7.2. Treatment Period (Day 1 to Day 84 ± 4)

7.2.1. Visit 2 (Day 1/Confirmatory and Randomization Visit)

Procedures performed at Visit 2/Day 1 include:

- Concomitant medication review
- Urine pregnancy test (women of childbearing potential only)
- SANDE
- Individual symptom assessment (VAS)
- IP comfort assessment
- BCVA (logMAR)
- Biomicroscopy/external eye exam
- TBUT
- Corneal fluorescein staining
- Conjunctival lissamine green staining
- Anesthetized Schirmer's test
- Review inclusion/exclusion criteria
- Randomize eligible subjects
- Dispense IP/provide instruction on administration
- Dispense artificial tears (if needed)
- AE assessment
- Run-in medication accountability
- Artificial tear accountability, if applicable

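### Does calling the run-in vehicle IP mean that treatment-emergent events and the safety population start at the Visit 1 run-in dose?

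*Protocol*

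**What the plan says.** Section 9.6.2 defines the treatment-emergent adverse event (TEAE) in one unqualified sentence: "A TEAE will be defined as occurring after the first dose of IP". The paragraph immediately before it says that events between Visit 1 and Visit 2 "will be summarized separately from AEs that occur from the first dose of double-masked treatment on Day 1". Section 6.6 sets the same boundary, with the second group being "AEs that occur from the first dose of double-masked treatment on Day 1 to the Day 84 Visit or Early Discontinuation".

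Section 9.3.3 and the synopsis define the safety population as all who received IP, analysed as treated, without mentioning randomization. Section 9.3.1 requires both randomization and receipt of IP for the intent-to-treat (ITT) population.

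A note in Section 6.4.1.1 makes IP cover the vehicle as well as each strength of SDP-4, with no exception for the run-in. Section 5.9 states that at Visit 1 "vehicle solution for the screening/run-in period will be dispensed to the subject with instructions to return the used and unused IP". Section 5.2 says that "the used and unopened IP will be documented at Visits 2 through 7", although only run-in supply can come back at Visit 2. Section 5.7, which opens by describing how IP is filled, includes the box with "a total of 35 SUDs for the 2-week run-in period".

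**The concern.** A term used in two senses feeds three definitions. If run-in vehicle is IP, three things follow from the literal text.

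- The TEAE window opens at the supervised run-in dose at Visit 1. An event that occurs before any exposure to SDP-4 could then be tabulated under an SDP-4 arm.
- A subject who took run-in vehicle and failed at Visit 2 has received IP and so meets the safety population definition. The as-treated rule would point to the vehicle column. Such failures are foreseeable, because Section 4.2 requires the entry criteria to be met again at Visit 2.
- Every randomized subject who used the run-in supply has already received IP. The clause in the ITT definition then no longer removes someone who was randomized but took no masked product.

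Section 9.6.2 makes TEAEs by treatment group the primary safety analysis, and Section 1 describes this as the first study in humans. The event window and denominator of that analysis should not depend on how a reader takes an abbreviation.

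**Working it through.** **Inputs.** Masked treatment lasts 84 days (Section 5.2). The run-in lasts 14 ± 2 days on twice-daily vehicle (Sections 3.1 and 5.1.2). The run-in box holds 7 cartridges of 5 single-use doses (Section 5.7). Planned randomization is 300 subjects, 75 per arm (Section 4.1).

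**1. Run-in exposure.** The stated supply reproduces: 7 × 5 = 35 units. Twice-daily use needs 2 × 14 = 28 units (2 × 12 = 24 to 2 × 16 = 32), which 35 covers. Subjects therefore do take vehicle for about two weeks before Day 1, and the question is a real one.

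**2. Length of the window.**
- Narrow reading: 84 days.
- Broad reading: 84 + 14 = 98 days (84 + 12 = 96 to 84 + 16 = 100).
- Share before randomization: 14/98 = 14.3% (12/96 = 12.5% to 16/100 = 16.0%).

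These are days, not events. The protocol gives no run-in event rate, so no number of events follows.

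**3. Which reading fits the other sentences?** The only events in dispute are those between Visit 1 and Day 1. Sections 6.6 and 9.6.2 assign that interval to its own summary. Under the broad reading such an event would appear both there and in the TEAE table, which breaks the separation rule. Under the narrow reading it appears once. Only the narrow reading satisfies all the sentences together.

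**4. How the term is used across the document.**
- Broad: the note in Section 6.4.1.1, the return and accountability phrases in Sections 5.9 and 5.2, and the packaging text in Section 5.7.
- Narrow: the synopsis and Section 3.1 give IP for 84 days and describe the vehicle run-in separately. Section 5.6.2 contrasts run-in vehicle with randomized IP. Table 1 has one row for dispensing run-in medication (Visit 1) and another for dispensing IP (Visits 2, 5 and 6), and its accountability row names the two as separate items. Section 7.2.1 lists run-in medication accountability at Visit 2, while Sections 7.2.4, 7.2.5 and 7.3 list IP accountability.

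Apart from the note in Section 6.4.1.1, the broad uses concern supply and returns. The text that governs dosing and the visit schedule uses the narrow sense.

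**5. Safety population.** The literal reading would add run-in failures. The protocol gives no failure rate. If a fraction f of subjects dosed in the run-in were not randomized, the extra number is 300/(1 − f) − 300. As assumptions only, f = 10%, 20%, 30% and 50% give about 34, 75, 129 and 300 subjects. At 20%, putting them all under vehicle would make that column 75 + 75 = 150 against 75 in each SDP-4 arm. That layout would be conspicuous. It also sits badly with TEAE tables by treatment group, and with Section 6.9, which classes subjects who fail the criteria and are not randomized as screen failures.

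**6. ITT population.** Randomization is still required, so no run-in failure enters. The only subject affected is one who is randomized and never takes masked product. The mixed model in Section 9.5.3 analyses change from baseline over visits, so such a subject contributes nothing to it without a post-baseline score. Keeping a subject who does have one moves the set closer to all randomized subjects, which does no harm.

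**7. Effect on inference.** The safety analysis is descriptive. All arms get the same vehicle before randomization, so run-in events are balanced across arms in expectation. The sample size (70 + 5 = 75 per group, 4 × 75 = 300) and the six-step testing order do not use these definitions.

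**The case for a change.** The strongest case for acting is that this is the protocol's own wording and not a detail left to the SAP. The definitions are stated here, the note on IP sits in the adverse event section itself, and Section 5.1.2 describes the run-in supply under the heading for the control. A programmer working from Section 9.6.2 alone could start the window at Visit 1. A run-in event judged related to IP would then count as treatment-related under an SDP-4 arm. Aligning the sentences would cost almost nothing.

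Two parts of this stand. The safety population sentence does not say randomized, whereas the ITT sentence does. The TEAE sentence does not repeat the Day 1 anchor. Both are drafting weaknesses.

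The rest is weaker. Nobody can take the TEAE sentence from Section 9.6.2 without passing the paragraph that sets the Day 1 boundary. The ITT argument touches an unusual subject who has little or no weight in the primary model. The "IP comfort assessment" listed at Visit 2 may refer to run-in vehicle if no masked dose is given in clinic that day, but it bears on neither the event window nor the populations.

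**Conclusion.** The ambiguity is real as wording and has no demonstrated effect on the analysis. Read as a whole, the protocol gives one workable answer: treatment-emergent events count from the first masked dose on Day 1, run-in events are shown separately, and the by-arm safety tables contain randomized subjects who were dosed. An analyst would program it that way without an amendment.

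The most the misreading could do is open the window 12 to 16 days early and add subjects without an assigned arm, and each step would contradict text elsewhere in the protocol. No power, alpha, sample size or efficacy conclusion changes. This conclusion assumes that the separation rule in Sections 6.6 and 9.6.2 is applied as written and that safety tables are laid out by randomized arm. It does not rest on any assumed run-in event or failure rate.

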3. INVESTIGATIONAL PLAN

3.1. Overall Study Design and Plan

This is a Phase 2, multicenter, double-masked, randomized, vehicle-controlled, dose-response, parallel-group study designed to evaluate the ocular and systemic safety and efficacy of SDP-4 ophthalmic solution in subjects with moderate to severe DED in both eyes (OU) over a 12-week (84-day) treatment period.

Subjects will be randomized to 1 of 3 concentrations (0.1%, 1.0% and 3.0%) of SDP-4 Ophthalmic Solution or vehicle in a 1:1:1:1 ratio in parallel groups. All investigational product (IP) (SDP-4 concentrations and vehicle) will be provided in single-use dose (SUD) containers seal packed into foil pouches. Subjects, the Investigator, and all site personnel responsible for performing study assessments will remain masked to treatment assignment.

The IP will be administered via topical ocular instillation, one drop per eye, twice daily (BID) for 12 weeks (84 days). Both eyes will be treated. A 2-week screening/run-in period on BID vehicle will precede the 12-week randomized treatment period.

Subjects must have a Symptom Assessment in Dry Eye (SANDE) total score of ≥ 40 at Visit 1/Screening and Visit 2/Day 1 to enter the trial. For subjects with a qualifying SANDE score who meet all other inclusion/exclusion criteria, the eye with the lower tear break-up time (TBUT) at Visit 2/Day 1 will be designated as the study eye. In the event both eyes have the same TBUT scores, the eye with the lower Schirmer's test score will be designated as the study eye. If both eyes have the same TBUT and Schirmer's test scores, the right eye will be designated as the study eye.

The study will consist of 7 clinic visits, 2 visits during the screening period and 5 on-treatment visits: Visit 1 (Day -14 ± 2 /Screening Visit), followed by the 2-week run-in period on BID vehicle, Visit 2 (Day 1/Confirmatory and Randomization Visit), Visit 3 (Day 7 ± 2), Visit 4 (Day 14 ± 2), Visit 5 (Day 28 ± 2), Visit 6 (Day 56 ± 4) and Visit 7 (Day 84 ± 4 /End of Study Assessments).

If a subject complains of persistent dry eye symptoms, the site may provide the subject with unpreserved artificial tears (provided by the Sponsor), to be used only if necessary. The subject must return all used and unused artificial tears at each visit so the site can conduct accountability to assess the use of artificial tears. Artificial tears may not be used within 2 hours prior to any study visit.

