6.8. Other Safety Assessments

6.8.1. Best-Corrected Visual Acuity

Best-corrected visual acuity (BCVA) measurement will be performed in each eye at all study visits with the logMAR eye chart using the subject's best corrective lens prescription eyeglasses or trial frame lenses, if applicable. The subject's BCVA must be determined (via refraction) if corrected or uncorrected visual acuity is not logMAR 0.0 (equivalent to 20/20). This refraction must be used for all VA assessments for the duration of the study. The subject must wear the same glasses/trial frame, if applicable, at each visit. Ambient room lighting should be consistent for a given subject throughout the study period. Consult the Study Reference Manual for specific details regarding the evaluation procedures.

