6.8.4. Intraocular Pressure Measurement

Intraocular pressure will be measured utilizing a Goldmann tonometer. If possible, the same observer should perform the assessment and the same calibrated instrument should be used for a given subject throughout the study. To avoid IOP changes due to the diurnal rhythm, the

IOP measurements should be performed at approximately the same time of the day each time. Consult the Study Reference Manual for specific details regarding the evaluation procedures.

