9. STATISTICS

9.1. General Considerations

This is a Phase 2, multicenter, randomized, double-masked, vehicle-controlled, dose-response, parallel group study to evaluate the ocular and systemic safety and efficacy of SDP-4 ophthalmic solution in subjects with moderate to severe DED.

Subjects with DED are planned to be randomized to 1 of 3 concentrations of SDP-4 (0.1%, 1.0%, or 3.0%) or vehicle in a 1:1:1:1 ratio, with 75 subjects randomized to each group.

A biostatistician will perform statistical analyses as agreed with the Sponsor according to the Statistical Analysis Plan (SAP).

All continuous study assessments will be summarized by treatment and visit (as applicable) using descriptive statistics (n, mean, median, standard deviation, minimum, and maximum). All categorical study assessments will be summarized by treatment and visit (as applicable) using frequency counts and percentages.

All study data will be listed by treatment, subject, and visit (as applicable).

The unit of analysis for efficacy will be the study eye.

Efficacy analysis will be conducted on the intent-to-treat (ITT) population (primary efficacy analysis) and the per protocol (PP) population (secondary efficacy analysis). Safety analyses will be performed using the safety analysis population. Definitions for the analysis populations may be found in Section 9.3.

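### The by-group proportion of BCVA losses and IOP rises is confined to study eyes, although both eyes are treated and the study eye is an efficacy unit

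*Protocol*

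**What the plan says.** Section 9.6.2 summarises BCVA and IOP at each visit and includes "the proportion of study eyes with pre-defined increases from baseline, specifically, eyes with a 3-line decrease in BCVA or eyes with" an IOP rise of 10 mm Hg or more.

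Other sections bear on that choice:

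- Section 3.1 defines the study eye as one eye per subject: the eye with the lower TBUT at Visit 2, then the lower Schirmer's score, then the right eye.
- Section 9.1 gives that eye its purpose: "The unit of analysis for efficacy will be the study eye". No section makes it the unit for safety.
- Section 3.1 also states: "Both eyes will be treated". Section 5.2 has both eyes dosed twice daily for 84 days.
- Section 6.8.1 says of BCVA that "measurement will be performed in each eye at all study visits".
- Section 9.6.2 summarises treatment-emergent adverse events "using discrete summaries at the subject level by system organ class and preferred term for each treatment group", with no restriction by eye.

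**The concern.** A unit chosen for efficacy, on tear-film status, has been carried into a safety table without a stated reason. The protocol does not connect lower TBUT with the risk of losing acuity or of a pressure rise. The fellow eye receives the same product on the same schedule, so it is just as relevant to safety.

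This is the only by-group proportion of threshold BCVA and IOP changes that the protocol plans from the measurements themselves. A change confined to the fellow eye would not be counted in it. The other route to a by-group count is the adverse event tables, and that depends on the investigator. Section 6.6 says "Investigators are advised to consider reporting an increase in IOP of 10 mmHg or greater" and treats a three-line loss of acuity in the same way, which is advice and not a rule.

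The study is first-in-human (Section 1) and its primary objective names safety (Section 2.1), so an incomplete count of threshold changes is worth correcting even though nothing inferential depends on it.

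**Working it through.** **Plan's own figure.** The protocol states no figure for this table. Its one power statement, 70 per group for 80% power (Section 9.2), reproduces: a two-sided t-test at 0.05 with difference 11.684 and SD 24.5 has power 0.800 at n = 70. This point does not touch it.

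**Coverage.** Section 9.1 plans 75 subjects per group.

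- Treated eyes per group: 75 × 2 = 150.
- Eyes in the table as written: 75.
- Eyes outside it: 150 − 75 = 75, or half.

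**Assumptions.** The documents give no rate of threshold events per eye and no between-eye correlation. Let p be the chance of an event in one eye over whatever period the table covers, taken as equal for study and fellow eyes, and phi the correlation between the two eyes of a subject. I take p = 0.5%, 1% and 2%, and phi from 0 to 1.

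**Formulas.**

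- Chance of an event in either eye: q = 2p − [p² + phi·p(1 − p)].
- Share of affected subjects missed by a study-eye table: (q − p)/q.
- Chance that the table shows at least one event in a group of 75: 1 − (1 − p)^75 for study eyes, 1 − (1 − q)^75 for either eye.

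**Worked case, p = 1%, phi = 0.5.** q = 0.02 − [0.0001 + 0.5 × 0.0099] = 0.01495. Share missed = (0.01495 − 0.01)/0.01495 = 33%. Chance of at least one event: 1 − 0.99^75 = 53% for study eyes, against 1 − 0.98505^75 = 68% for either eye.

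**Share of affected subjects missed (p = 1%; almost the same at the other rates).**

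| phi | 0 | 0.25 | 0.5 | 0.75 | 1 |
|---|---|---|---|---|---|
| Share missed | 50% | 43% | 33% | 20% | 0% |

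**Chance that this table shows at least one event in a group of 75.**

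| Rate per eye | Study eye only | Either eye, phi 0 | phi 0.25 | phi 0.5 | phi 0.75 | phi 1 |
|---|---|---|---|---|---|---|
| 0.5% | 31% | 53% | 48% | 43% | 38% | 31% |
| 1% | 53% | 78% | 73% | 68% | 61% | 53% |
| 2% | 78% | 95% | 93% | 90% | 85% | 78% |

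With the 70 per group that Section 9.2 expects after discontinuations, the 1% row at phi 0 becomes 1 − 0.99^70 = 51% against 1 − 0.99^140 = 76%. The share missed does not depend on group size.

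These figures describe this one table, not the chance that the trial as a whole would notice an event.

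**The case against.** The strongest reply is that the sentence in Section 9.6.2 is not exhaustive. It presents the study-eye proportion as one item included in a wider BCVA and IOP summary that itself carries no eye limit, so a fellow-eye column would comply with the protocol. This is true, but the text permits such a column without planning it. The one proportion it does specify names study eyes.

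A second reply is that one eye per subject gives independent units and a clean denominator, and that table layout is usually left to the SAP. The first part is fair, but counting subjects with an event in either eye gives the same clean denominator without discarding treated eyes. On the second, the protocol has not left the matter open.

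A third is that fellow-eye safety is covered elsewhere: subject-level adverse events, biomicroscopy and fundus shift tables with no eye limit, listings of all data, and the minimum and maximum required by Section 9.1 for continuous assessments. This stands, and it limits the importance of the point. Even so, listings give no rate by group, an extreme value is not a count, and adverse event reporting of these changes is discretionary.

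Finally, the size rests on assumed rates and correlations. Both eyes get the same treatment, so full independence is an extreme case and the true loss may be well below one half. That also stands, which is why the range runs down to zero.

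**Conclusion.** The point holds. As written, the threshold proportion covers half of the treated eyes, 75 of 150 per group, using a unit that the protocol assigns to efficacy, and no reason is given. The share of affected subjects it would miss lies between 0% and about 50%, depending on a between-eye correlation that the documents do not supply; it is about one third at phi 0.5. That range also assumes that study and fellow eyes share the same event rate.

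The consequence is an incomplete descriptive safety summary. No hypothesis test, stopping rule or sample size depends on it, and fellow-eye data are not lost. It should be changed because the improvement is real and costs almost nothing.

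**What to change.** In Section 9.6.2, replace the study-eye proportion with the proportion of subjects who have the event in either treated eye, by treatment group and visit, and add counts for study eyes and fellow eyes separately. Counting subjects also deals with the correlation between eyes.

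The cost is one changed sentence and a few extra table columns. BCVA is already collected in each eye. For IOP, Section 6.8.4 says only "Intraocular pressure will be measured utilizing a Goldmann tonometer" and refers to the Study Reference Manual for details, so the sponsor should confirm that both eyes are recorded before applying the either-eye definition to IOP. Sample size and efficacy analyses are unaffected.
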